# 4.3. Primary Estimand Analysis

Treatment comparisons between each LY3972406 dose and placebo in the proportion of participants achieving PASI 75 at Week 12 will be analyzed using the Cochran-Mantel-Haenszel

test stratified by prior exposure to biologic therapy for psoriasis (biologic naïve versus experienced) with NRI, as described. Participants who fail to complete the 12-week treatment period due to an ICE related to study intervention or violate the concomitant medications rules will be treated as nonresponders. The 95% confidence intervals associated with the treatment response rate and treatment difference to placebo will be provided by treatment. The primary analysis will be conducted on the modified intent-to-treat analysis set when all participants reach Week 12 or have discontinued during the treatment period.

## 4.4. Secondary Estimands Analysis

Proportions of participants achieving the following scores will be analyzed using the Cochran-Mantel-Haenszel test stratified by prior exposure to biologic therapy for psoriasis (biologic naïve versus experienced) with NRI:

- PASI 90
- PASI 100
- sPGA 0 (clear)
- sPGA 0 or 1 (clear or almost clear)
- PSSI 0

Participants who fail to complete the 12-week treatment period due to an ICE related to study intervention or use prohibited concomitant medications will be treated as nonresponders. The 95% confidence intervals associated with the treatment response rate and treatment difference will be provided by treatment.

Treatment comparisons between each LY3972406 dose and placebo in the PASI percent change, body surface area mean change from baseline, PSSI mean change from baseline to Week 12, and patient reported outcomes will be analyzed using the MMRM model, as described in Section 4.1. No missing data imputation will be performed. The least squares mean and 95% confidence interval will be summarized by treatment.

# 4.5. Pharmacokinetic and Pharmacokinetic and Pharmacodynamic Methods

Plasma concentrations of LY3972406 will be summarized by time point and dosing regimen using descriptive statistics.

Additional analyses may be conducted as deemed necessary on review of the data. For example, graphical analyses, model-based pharmacokinetic (PK) analyses, or both may be conducted. Exposure-response analysis between LY3972406 concentrations and clinical efficacy endpoints, pharmacodynamic (PD) or biomarker endpoints, or both may be performed using population PK and PD nonlinear mixed-effects modeling techniques implemented in NONlinear Mixed Effects Modeling (NONMEM®) or Monolix® software.

Additionally, the impact of intrinsic and extrinsic factors, such as age, weight, gender, and renal function, on model parameters may be examined as needed.

## 4.6. Exploratory Analysis

The exploratory endpoints include

# 4.7. Safety Analyses

All safety data will be descriptively summarized by treatment groups (LY and placebo) and analyzed based on the safety population described in Section 3. The safety will be assessed by evaluating AEs, laboratory analytes, vital signs, ECGs, special safety topics, and the CCI.

Additional analysis may be included if applicable. The duration of exposure will also be summarized.

The treatment period safety analyses will compare each and combined doses of LY3972406 to placebo; treatment group comparisons will be analyzed using the methods described in Section 4.1. Summaries of safety data collected during the follow-up period will be presented separately. Safety analyses will be conducted on the safety analysis set.

## 4.7.1. Extent of Exposure

Duration of exposure to study drug during the double-blind treatment period will be summarized by treatment arm. Duration of exposure on treatment will be calculated as the date of last dose of study drug (or date of discontinuation) minus the date of first dose of study drug plus 1 day. Total patient-years of exposure will be reported for each treatment group for overall duration of exposure. Descriptive statistics (number of participants in the analysis [subset] population, mean, standard deviation, minimum, maximum, first quartile, median, third quartile, and maximum) will be provided for patient-days of exposure.

Overall exposure will be summarized in total patient-years, which will be calculated as follows:

Exposure in patient years =  $Sum \ of \ duration \ of \ exposure$  (for all patients in treatment arm) / 365.25.

No inferential analysis for comparison between treatment arms will be performed.

#### 4.7.2. Adverse Events

AEs are recorded in the electronic case report forms (eCRFs). Where changes in severity are recorded in the eCRF, each separate severity of the AE will be reported in the listings. Only the most severe will be used in the summary tables.

AEs will be coded according to the current version at the time of database lock of the Medical Dictionary for Regulatory Activities (MedDRA). The MedDRA lowest level term will be used in defining which events are treatment-emergent (TE). The severity of AEs is recorded as mild, moderate, or severe. The maximum severity for each lowest level term during the baseline period will be used as baseline. Baseline for the double-blind treatment period is defined as all preexisting conditions recorded at Visit 1 and any AEs recorded before the first dose of study intervention. The treatment period will be included as postbaseline for the analysis. For events with a missing severity during the baseline period, it will be treated as 'mild' in severity for determining treatment-emergence. Events with a missing severity during the postbaseline period will be treated as 'severe,' and treatment-emergence will be determined by comparing to baseline severity. For events occurring on the day of first taking study medication, the start times of the study treatment and AE will be used to determine whether the event was pre- versus posttreatment. If the start time for the AE is missing, it will be assumed to have started in the later period.

A TEAE is defined as an event that first occurred or worsened in severity after baseline and on or prior to the date of the last visit within the treatment period. For each event classification term, the number of participants experiencing a TEAE with that classification term will be tabulated. A follow-up emergent AE is defined as an event that first occurred or worsened in severity after Week 12 (Visit 9) or early discontinuation. For events that are gender-specific, the denominator and computation of the percentage will include participants only from the given gender. A preexisting condition is defined as a condition that starts before the participant has provided written informed consent and is ongoing at consent. A non-TEAE is defined as an AE that starts after informed consent but prior to the first dose. Further definitions and information for AEs can be found in FVAA Protocol in Section 8.3 and in Appendix 3, Section 10.3.

In an overview table, the number and percentage of subjects who experienced a TEAE or SAE, died due to an AE, or discontinued from the study due to an AE will be summarized by treatment.

An overall summary of AEs will be provided for the population, treatment period, severity, and relationship to the study drug. The number of TEAEs, the number of participants experiencing a TEAE, and the percentage of participants experiencing a TEAE will be summarized by population, treatment, and MedDRA system organ class (SOC) and preferred term (PT). The MedDRA version is documented in the Data Management Plan. This includes the number and percentage of participants who experienced TEAEs, TEAEs by maximum severity, deaths, SAEs, TEAEs related to study intervention, and AEs leading to discontinuation of study intervention. The summary and frequency AE tables will be presented for all causalities and

those considered related to the study drug by the clinician. Any serious AEs will be listed. AEs by day of onset will be presented.

The number and percentage of patients with TEAEs will be summarized by treatment group in the 2 formats listed below:

- by MedDRA PT nested within a SOC, with SOCs ordered alphabetically and events ordered within each SOC by decreasing frequency in the treatment group, and
- by MedDRA PT with events ordered by decreasing frequency in the treatment group.

AEs leading to permanent discontinuation of study drug and AEs leading to temporary interruption of study drug will also be summarized by treatment group using MedDRA PT nested within SOC.

Follow-up emergent AEs, SAEs including deaths, and AEs leading to study discontinuation will be summarized for the posttreatment follow-up period.

Listings will be presented for all AEs, all SAEs, all AEs leading to death, all AEs leading to study drug temporary interruption, and all AEs leading to discontinuation from the study.

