Fasting visit		X							X	Participants should not eat or drink anything except water for 12 hours before the visit.
										study intervention. See Section 8.2.8 and Appendix 7, Section 10.7.
HIV screening tests	X									
Hepatitis C Virus (HCV) screening tests	X									If HCV antibody test is positive, it must be followed by an HCV RNA test. See Section 8.2.10.
Hepatitis B Virus (HBV) screening tests	X									Includes testing for HBsAg and anti-HBc. See Section 8.2.9.
HBV DNA	X								X	Only for participants who are positive for anti-HBc at screening. See Section 8.2.9.
CCI										
C-reactive protein, high-sensitivity (hsCRP)		X							X	
Pharmacokinetic (PK) samples (predose)		X			X	X	X		X	Starting at Visit 5, for each PK sample collected, record time and date of previous dose administration.
Pharmacokinetic (PK) samples (postdose)		X		X					X	For each PK sample collected, record time and date of previous dose administration. At Visit 2 and Visit 9, collect 2 PK samples: one in the period of 0.5 to 2 hours and one in the period of 3 to 4 hours postdose. At Visit 4 collect at any time postdose. All actual sample dates and times should be recorded.
Stored samples										
Genetics sample		X								Sample can be obtained at or after the specified visit.

Study J4H-MC-FVAA	Screening		D	ouble-I	Blind T	reatme	Comments			
Visit number	1	2	3	4	5	6	7	8	9	
Weeks from randomization	≤5		1	2	4	6	8	10	12	
Visit interval tolerance (days)	≤35		±3	±3	±3	±3	±3	±3	±3	
Fasting visit		X							X	Participants should not eat or drink anything except water for 12 hours before the visit.
CCI										
Skin biopsy		X							X	Optional  Visit 2: 1 biopsy each of lesional and non- lesional skin.  Visit 9: 1 biopsy of lesional skin.  See Appendix 10, Section 10.10
Randomization and dosing										
Register visit with IWRS	X	X	X	X	X	X	X	X	X	
Randomization via IWRS		X								
Dispense study intervention to participant (for at home dosing)		X			X		X			
Observe participant administer study intervention		X		X	X		X		X	Participants will be instructed to withhold study intervention on study visit days, until after predose laboratory samples have been collected.
Participant brings study intervention			X	X	X	X	X	X	X	
Assess study intervention compliance			X	X	X	X	X	X	X	

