# 7.3. Lost to Follow-up

A participant will be considered lost to follow-up if he or she repeatedly fails to return for scheduled visits and is unable to be contacted by the study site. Site personnel or designee are expected to make diligent attempts to contact participants who fail to return for a scheduled visit or were otherwise unable to be followed up by the site.

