#### Adverse events analyses

Adverse events will be coded according to the Medical Dictionary for Regulatory Activities. A TEAE is defined as an event that first occurred or worsened in severity after baseline and on or prior to the date of the last visit within the treatment period. A follow-up emergent adverse event (FEAE) is defined as an event that first occurred or worsened in severity after Week 12 (Visit 9) or the ED. For events that are gender specific, the denominator and computation of the percentage will include participants only from the given gender.

An overall summary of AEs will be provided for the treatment period, including the number and percentage of participants who experienced TEAEs, TEAEs by maximum severity, deaths, SAEs, TEAEs related to study intervention, and AEs leading to discontinuation of study intervention.

Follow-up emergent AEs, SAEs including deaths, and AEs leading to study discontinuation will be summarized for the post-treatment follow-up period.

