# 3. Analysis Sets

For purposes of analysis, the following populations are defined:

Population	Description
Screening	All patients who signed informed consent.
Modified intent-to-treat (mITT)	All participants randomly assigned to study
	intervention and who take at least 1 dose of study
	intervention. Participants will be analyzed
	according to the study intervention to which they
	were assigned.
Per-protocol	All randomized participants who do not commit an
	important protocol deviation that could potentially
	compromise efficacy results.
	Participants will be analyzed according to the
	study intervention to which they were assigned.
Safety	All randomized participants who received at least
	1 dose of study intervention.
	Participants will be analyzed according to the
	study intervention they received.
Pharmacokinetic (PK)	All participants randomly assigned to study
	intervention and who take at least 1 dose of study
	intervention and have PK data available.
Follow-up	All mITT participants who have entered the
	posttreatment follow-up period.
	Participants will be analyzed according to the
	study intervention to which they were assigned.

**Note:** In the context of this table and throughout the protocol, the terms "study intervention" and "treatment" may be used interchangeably.

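### Without a Visit 9 or a qualifying ED visit, on-drug adverse events after the last treatment-period visit can fall outside both the treatment-emergent and follow-up emergent windows

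*SAP*

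**What the plan says.** SAP 4.7.2 and Protocol 9.3.5 give the same end to the TEAE window: the event must occur or worsen after baseline and "on or prior to the date of the last visit within the treatment period".

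The start of the follow-up emergent window differs slightly between the two:
- SAP 4.7.2: "an event that first occurred or worsened in severity after Week 12 (Visit 9) or early discontinuation".
- Protocol 9.3.5: "an event that first occurred or worsened in severity after Week 12 (Visit 9) or the ED".

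Neither document says which date early discontinuation takes. It could be the ED visit, the day drug stopped, or the day of study disposition. Neither says whether the ED visit lies within the treatment period. The ED visit is scheduled in Protocol 1.3.2 with unscheduled and follow-up visits, not in the treatment-period schedule of Protocol 1.3.1.

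Other provisions bear on this:
- Protocol 1.3.1 dispenses drug for home use at Visits 2, 5 and 7 (Weeks 0, 4 and 8).
- SAP 4.7.1 measures exposure as "the date of last dose of study drug (or date of discontinuation) minus the date of first dose of study drug plus 1 day".
- Protocol 7.2 asks for an ED visit on leaving the study only where this is possible.
- Protocol 7.3 covers a participant who "repeatedly fails to return for scheduled visits and is unable to be contacted by the study site".
- Protocol 8.3.1 collects AEs until study participation ends.

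**The concern.** Exposure follows dosing, but the TEAE cut-off follows visits. Someone who keeps dosing at home after the last treatment-period visit accrues exposure on days when no event can be treatment-emergent. If Visit 9 and a qualifying ED visit are both absent, nothing in the text opens the follow-up window at that last visit, so the two windows need not meet.

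TEAE incidence is a named safety endpoint. The TEAE flag also drives the SOC and preferred-term tables, the severity and relatedness tables, the treatment-emergent infection tables (serious infections included), and the search for potential opportunistic infections in SAP 4.7.4.1. If some of these events are themselves the reason a participant stops attending, the omission is selective.

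**Working it through.** The documents give no figure for this point, so there is nothing to reproduce. The check applies the two definitions literally to dated cases and then sizes the uncovered time.

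**1. Classification.** With first dose on day 1, Week 8 (Visit 7) is day 8 × 7 + 1 = 57, Week 10 (Visit 8) is day 71 and Week 12 is day 85. Main case: last treatment-period visit on day 57, last dose on day 84, AE onset on day 70. Day 70 is later than day 57, so the event is not a TEAE. Whether it is follow-up emergent depends on the meaning given to early discontinuation:

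| Meaning of early discontinuation | Follow-up window opens after | Day-70 event |
|---|---|---|
| ED visit, never held | never | neither window |
| Day drug stopped | day 84 | neither window |
| Later disposition date, e.g. day 100 | day 100 | neither window |
| Back-dated to last attended visit | day 57 | follow-up emergent, although on drug |

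Two variants:
- An ED visit is held on day 80. If it counts as a treatment-period visit, the event is a TEAE. If it does not, the event is in neither window.
- Visit 9 is missed but Visit 801 is attended, the last treatment-period visit is Visit 8 (day 71), onset is on day 80, and the follow-up window is taken to open at nominal Week 12 (day 85). The event is in neither window.

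**2. Mismatch with exposure.** In the main case exposure is 84 − 1 + 1 = 84 days, while the TEAE window ends on day 57. So 84 − 57 = 27 exposure days (27/84 = 32%) cannot produce a TEAE.

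**3. Uncovered on-drug time.** The quantity dispensed is not stated; assume it lasts to the next dispensing visit, or to Week 12 after Visit 7. Then uncovered time = (week supply ends − week of last visit) × 7 days.

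| Last visit | Week | Supply ends | Uncovered |
|---|---|---|---|
| 2 | 0 | Week 4 | 28 days |
| 3 | 1 | Week 4 | 21 days |
| 4 | 2 | Week 4 | 14 days |
| 5 | 4 | Week 8 | 28 days |
| 6 | 6 | Week 8 | 14 days |
| 7 | 8 | Week 12 | 28 days |
| 8 | 10 | Week 12 | 14 days |

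These are nominal-schedule figures; the ±3-day visit windows can shift them by a few days.

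**4. Chance of an event in the gap.** The documents give no AE rate. Assume a 12-week incidence p of 30% to 60% with constant hazard. The chance of at least one AE in g days is 1 − (1 − p)^(g/84).
- g = 14: 1 − 0.7^(1/6) = 6% to 1 − 0.4^(1/6) = 14%.
- g = 28: 1 − 0.7^(1/3) = 11% to 1 − 0.4^(1/3) = 26%.

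These are per affected participant who keeps dosing through the gap, and the event must still reach the site.

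**The case against.** The strongest reply is that the events that matter most are counted anyway. SAP 4.7.2 puts SAEs, deaths due to an AE and study discontinuations due to an AE in the overview table by treatment. It also summarises AEs leading to permanent discontinuation or interruption of drug by SOC and preferred term, and lists every AE. None of these is stated to be limited to the TEAE window. This stands. A reader might infer that deaths and hospitalisations drop out of the summaries or survive only in listings; the SAP does not support that.

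A reader might also infer that the Follow-up set ("All mITT participants who have entered the" post-treatment period) excludes these participants from the follow-up AE tables. That is not supported either. SAP 4.7 and Protocol 9.3.5 place safety analyses on the safety set.

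A third reply is that the last treatment-period visit could mean the scheduled Week 12 visit, so that the windows meet. The wording is loose enough to allow the thought, but the rule needs a visit date and a missed visit has none.

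The affected group is small, and this too stands. Protocol 7.1.3 keeps those who stop drug in the study for an ED visit and follow-up, Protocol 7.2 expects discontinuation to be uncommon, and someone who truly cannot be contacted will often report nothing.

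Two larger figures are tempting and should not be used:
- A gap of 14 + 3 + 3 = 20 days between consecutive later visits is uncovered only if no later treatment-period visit takes place. Otherwise that visit extends the window over it.
- A shift of 1/30 to 1/20 (3.3 to 5 points) in a TEAE rate per omitted participant assumes 20 to 30 per arm, which the public documents do not show, and applies only to someone with no other TEAE.

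**Conclusion.** The concern holds in a limited form. For participants with neither Visit 9 nor an ED visit counted as within the treatment period, an on-drug AE after the last visit is either in neither window or, if discontinuation is back-dated, labelled follow-up emergent. No reading of early discontinuation tested above makes it a TEAE.

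The damage is confined to outputs that use the TEAE flag. A serious infection in the gap, for example, would appear in the SAE count but not in the treatment-emergent serious infection table. The primary efficacy analysis is untouched.

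The upper size of about 28 days rests on three conditions: supply lasts to the next dispensing visit, dosing continues, and no later treatment-period visit is held. The number of participants cannot be derived from the documents and is probably small. The change is still worth making before unblinding, because the rule as written is incomplete and the repair is cheap.

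**What to change.** In SAP 4.7.2:
- End the TEAE window at the later of the last treatment-period visit date and the last dose date, and state that the ED visit counts as a treatment-period visit.
- If the last dose date is unknown, use a conservative imputed date no later than the earlier of the disposition date and the planned Week 12 date. The disposition date alone could fall well after dosing stopped and count off-drug events as treatment-emergent.
- Start the follow-up emergent window the next day, so that the windows are contiguous.
- Define the early-discontinuation date.

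In the main case above the TEAE window would then run to day 84 and follow-up would start on day 85, so the day-70 event is a TEAE.

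Protocol 9.3.5 carries the same TEAE definition and SAP 4.10 states that nothing has changed, so record the departure in SAP 4.10 and justify it in the clinical study report, as SAP 4.1 requires.

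The cost is SAP wording and a small programming change. No new data are needed, because Protocol 6.5 already records intervention start and stop dates. The downside is that a few more events may count as treatment-emergent.
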